The PROPHET trial is a prospective randomized double-blind placebo-controlled pilot study. During the study period, we intend to recruit post single or double lung transplantation patients expected to undergo bronchoscopy with TBLB as a part of their routine post-transplantation care. Study participants who meet inclusion and exclusion criteria will be randomized to receive prophylactic endobronchial topical epinephrine or placebo in a blinded manner prior to performance of TBLB. Bleeding complications of TBLB will then be assessed by the bronchoscopist at the time of the procedure and subsequently by two independent reviewers who will observe a video recording of the procedure. The bronchoscopist as well as the reviewers will be blinded to the study drug assignment. Additionally, patients will be monitored for potential adverse events associated with topical epinephrine instillation. In this trial, we intend to include a total of 100 procedures in the final analysis. The first 40 procedures will serve as a pilot for proof of concept, refinement of the protocol, and interim analysis of data for safety outcomes.

Eligibility Criteria

Inclusion Criteria

1. Male and female subjects, ≥ 18 years of age.
2. Single- or double-lung transplant recipients scheduled for bronchoscopy with TBLB.
3. Willingness to sign an informed consent for study participation.

Exclusion Criteria

1. Age <18 years.
2. Pregnancy.
3. Inability to understand and provide a written informed consent.
4. Exclusion criteria for TBLB
 - 4.1. Platelet count <50 K/microL.
 - 4.2. International normalized ratio (INR) >1.5.
 - 4.3. Known bleeding diathesis.
 - 4.4. Use of prophylactic or therapeutic dose of unfractionated heparin within 6 hours of the procedure.
 - 4.5. Use of prophylactic dose of low molecular weight heparin within 12 hours of the procedure.
 - 4.6. Use of therapeutic dose of low molecular weight heparin within 24 hours of the procedure.
 - 4.7. Use of oral direct thrombin inhibitors or oral factor 10a inhibitors within 48 hours of the procedure.
 - 4.8. Use of clopidogrel, ticlopidine, ticagrelor, or prasugrel within 5 days of the procedure.
 - 4.9. Uremia, defined as estimated glomerular filtration rate (eGFR) ≤30 mL/min.

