As described below, the next step is for a second team member to randomly select one set of labeled syringes without the first study team member knowing which was selected, and then log the selection. As such, the team remains blinded and only when the two logs are later merged will drug assignment be unblinded.

Study Group Randomized Assignment

To eliminate bias, two randomization and blinding processes will be employed: in preparing and labeling the sets syringes (as described above) and in choosing of the set of syringes at the time of the procedure. Those two separate processes will be performed by different members of the research team, each of them blinded to the results of the other procedure:

1. Two syringes will be prepared with the study drug (1:10,000 dilution of epinephrine) and two will be prepared with placebo (sterile saline). The syringes will be randomly labeled "A" and "B" based on a computerized electric coin toss and documented in a separate database as described above. This will be done by a member of the research team who will not be participating in the procedure and therefore blinded to the second randomization (syringe selection).
2. The syringes will be delivered to the procedure room prior to the procedure. At this time, the research team member who is responsible for the syringes will leave the room prior to the second randomization point.
3. The bronchoscopist or his/her assistant who is blinded to the drug and placebo preparation process will randomly choose "A" or "B" based again on a computerized electric coin toss.
4. The chosen set of syringes will be recorded as part of the study database.

Procedure Performance

1. Bronchoscopy will be performed in the controlled environment of the UMMC dedicated bronchoscopy suite under moderate sedation. The bronchoscopy suite in UMMC is routinely staffed by a nurse and a respiratory therapist in addition to the bronchoscopist and any trainees assisting with the procedure.
2. In addition to informed consent for participation in the study protocol, a formal UMMC informed consent for the performance of fiberoptic bronchoscopy, bronchoscopy-related procedures, and use of moderate sedation will be obtained.

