3. Per local protocol, peri-procedurally and during the procedure, the patient's heart rate, electrocardiography rhythm strip, respiratory rate, and oxygen saturation will be monitored continuously. Blood pressure will be repeatedly measured every 3 minutes. Up to 6 liters of supplemental oxygen via nasal cannula will be given in order to maintain an oxygen saturation of >92%. A defibrillator as well as a resuscitation drugs and equipment are available at all times in the bronchoscopy suite.
4. Patient will undergo the procedure in the supine position on an adjustable bed. Premedication will be performed per local protocol, including inhalation of 5 mL of 4% lidocaine via a nebulizer. Gurgling of 2 to 4 mL of 2% liquid lidocaine (20-40 mg) for upper airway anesthesia may also be applied depending on the performing bronchoscopist's preference. Moderate sedation will be achieved with a combination of midazolam (maximal dose of 6 mg per procedure) and fentanyl (maximal dose of 300 mcg per procedure). Laryngeal and lower airway anesthesia during the procedure will be obtained with the use of 2 mL aliquots of 2% liquid lidocaine up to a cumulative liquid lidocaine dose of 400 mg. A bite block will be used for procedures performed through the transoral approach. For the transnasal approach, 2% viscous lidocaine will be applied with a cotton swab to the chosen nostril and nasal passage to allow easy advancement of the bronchoscope.
5. Bronchoscopy will be performed with an Olympus BF-1T160 or BF-1TH190 (Olympus, Tokyo, Japan) video bronchoscope under fluoroscopic guidance (OEC 9900 Elite Mobile C-arm, GE Healthcare, Chicago, Illinois, United States).
6. For the purpose of independent post-procedure analysis, the entire procedure from insertion of the bronchoscope into the airways until its final retraction will be video-recorded on DVD media and individually labeled without disclosing study arm assignment. DVDs will be stored with other individual patient study documents for later review. Access to the stored DVDs will be provided only to the PROPHET study research team.

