7. Prior to biopsy performance 2 mL of 1:10,000 diluted epinephrine followed by 8 mL of ambient room air or 2 mL of sterile saline solution followed by 8 mL of ambient room air as described in "Study Drug and Placebo Preparation" will be instilled into the target airway by the bronchoscopist. This process may be repeated once, should the performing bronchoscopist choose to perform additional biopsy passes through a different airway. If choose to do so, the same study drug will be instilled into both airways. Any additional biopsies performed, will be done without airway instillation of study drug.
8. Biopsies will be performed using brand bronchoscopic biopsy forceps as preferred by the procedure performer. For ACR, aim will be to obtain 5 to 8 adequate biopsies, preferably from

the lateral subsegment of either the right or left lower lobes to allow optimal visualization and minimize forshortening under fluoroscopy as well as to avoid as much as possible spillage of blood into uninolved lung segments in the event of biopsy-related hemorrhage as described above. For the evaluation of radiological findings, aim will be to obtain 4 to 8 adequate biopsy specimens from an involved segment in one of the lungs based on imaging. All bronchoscopies will be performed by an experienced bronchoscopist.

9. The following data will be recorded with regard to the performance of the procedure:
 - 9.1. Patient study-arm assignment – recorded in a separate database.
 - 9.2. Indication for bronchoscopy with TBLB.
 - 9.3. Target number of TBLB specimens and target lobe and segment.
 - 9.4. Name and dosages of all medications administered to the patient in the hospital during the day of the procedure, including medications frequently administered during bronchoscopy such as topical anesthetic agents, sedation and analgesia agents, and hemostatic agents. Study drug vs. placebo administration will be recorded as described previously under “*Randomization*” and “*Study Drug and Placebo Preparation and Packaging*”.
 - 9.5. Supplemental oxygen requirements which exceed patient’s baseline requirements during or following the procedure.
 - 9.6. Any hemodynamic, cardiac, or respiratory events as recorded by telemetry in the procedure suite and/or in the recovery suite following the procedure.
 - 9.7. Bronchoscope model, including outer diameter and inner diameter of working channel.

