3. Acute closed angle glaucoma within 30 minutes of the instillation of the study drug.
4. New onset ECG changes suggestive of myocardial ischemia, including ST segment changes (defined: ≥ 1 mm ST segment elevation or ≥ 3 mm ST segment depression in ≥ 2 precordial or limb ECG leads that correspond together to one of the cardiac walls), new onset ventricular tachycardia, significant increase (≥ 10 per minute) in occurrence of ventricular ectopic beats, new onset supraventricular arrhythmia, new onset bundle branch block, and new onset 2nd or 3rd degree atrioventricular block, all occurring within 30 minutes of the instillation of the study drug.
5. Significant change in heart rate (defined as heart rate of >120 bpm and/or increase by ≥ 30 bpm above the baseline or heart rate <60 bpm and/or ≥ 30 bpm below the baseline) as recorded within 30 minutes of the instillation of the study drug.
6. Significant change in systolic blood pressure (defined as increase in systolic blood pressure >180 mm Hg and/or ≥ 40 mm Hg above the baseline; increase in diastolic blood pressure >110 mm Hg and/or ≥ 20 mm Hg above the baseline; or fall in systolic blood pressure <90 mm Hg and/or ≥ 20 mm Hg below the baseline) as recorded within 30 minutes of the instillation of the study drug.

Please refer to the section titled “Adverse Events Reporting and Data Monitoring” for further elaboration regarding reporting adverse events to the study monitoring committee. Please refer to the section titled “Adverse Events Reporting to the IRB” for further elaboration regarding reporting adverse events to the IRB.

Immediate Post-Procedure Surveillance

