1. All study participants' data will be anonymized and assigned a unique 5-character study identification number consisting of the first letter of the participants' last name, the first digit, and the last 3 digits of their UMMC medical record number. In a potential case where two different patients will be assigned the same study identification number, the first and last 4 digits of the UMMC medical record number will be assigned to both patients.
2. Individual PROPHET Study participant data will be collected in a designated study paper Case Report Form (CRF). Any information identified as Protected Health Information (PHI) will be kept separate from the participants CRF in a secure environment at UMMC accessible only to study staff allowed access to PHI. Each study participant CRF will also include the DVD media used for recording the bronchoscopy procedure.
3. All study collected data will be incorporated into computerized databases. Databases will be located behind UMMC network firewall on a UMMC server and accessible only under the following conditions:
 - 3.1 A workstation physically present in UMMC and physically connected to the network.
 - 3.2 Granted system access to database server.
 - 3.3 Granted password to the database folder(s).
 - 3.4 Granted password to the database item(s).
4. Computerized databases in use for the PROPHET study will include:
 - 4.1 Patient identifier and study drug assignment. This database will be accessible to investigators involved in study drug marking and blinded to the procedure and outcomes.
 - 4.2 All other study participant data collected as described above. This database will be accessible to investigators blinded to study drug assignment.
5. All study investigators will be trained and instructed not to export data to a standalone file, whether on laptops, hard drives, thumb drives, CDs, or any other media.

Data Analysis

Sample Size and Power Calculations

Formal power calculations are not possible as studies of this kind have not been previously performed and an aim of the study is to develop new bleeding assessment tools. As such, the first 40 procedures will provide data intended to show feasibility as well as to inform more refined power calculations. Numbers are based primarily on feasibility.

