Data are expressed as means with standard deviations, medians with interquartile range, percentages, and proportions as appropriate. Continuous outcome variables were visually examined for normality and outliers using histograms and scatter plots. The normal distribution was assessed with the Shapiro-Wilk test. Continuous variables were compared with the Student's t-test for normally distributed data with similar variance and the Mann-Whitney tests for non-normally distributed data. Proportions were compared using Chi-squared or Fisher's exact tests as appropriate. Statistical significance was set at $P<0.05$. All statistical analyses were performed based on original assigned groups and using Stata software, version 14 (Stata Corp LLC).

Potential Benefits

We hypothesize that prophylactic instillation of topical epinephrine prior to TBLB will reduce procedure-related hemorrhage, leading to lower rate of prematurely aborted procedure due to bleeding complications and higher yield of intended biopsies. The participants may, therefore, have direct benefit from participation if prophylactic topical epinephrine reduces the rate of procedure related hemorrhage in TBLB therefore avoiding early termination of procedure and more intended biopsies taken providing a higher diagnostic yield.

No financial reimbursements or incentive for participating in the PROPHET study will be provided.

Potential Risks and Discomforts

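### Heart rate and blood pressure are closely monitored, but the safety outcomes keep only yes/no events that pool rises with falls, so a systematic shift is easily missed

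*Combined protocol and SAP*

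**What the plan says.** Under Procedure Performance, item 3, heart rate is monitored continuously and "Blood pressure will be repeatedly measured every 3 minutes". A 30-minute window therefore holds about 30 / 3 = 10 blood pressure readings.

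Under Safety Outcomes, item 5 is a single yes/no outcome within 30 minutes of instillation: "Significant change in heart rate (defined as heart rate of >120 bpm and/or increase by" at least 30 bpm above baseline, or a rate below 60 bpm, or a fall of at least 30 bpm. Item 6 is built the same way. It combines high or rising systolic pressure, high or rising diastolic pressure, and low or falling systolic pressure.

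The data list under Procedure Performance, item 9.6, asks for "Any hemodynamic, cardiac, or respiratory events as recorded by telemetry in the procedure suite" or in recovery. It names no pre-instillation, serial, peak or lowest value. Aim 4 (Specific Aims) is exploratory, and its first element is the prevalence of clinically significant hemodynamic change.

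Under Data Analysis, "Proportions were compared using Chi-squared" or Fisher's exact tests. A general clause gives the t-test or Mann-Whitney test for continuous variables but ties neither to heart rate or blood pressure.

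**The concern.** Two features of items 5 and 6 cost information. First, each reduces a series of readings to whether a cut-off was crossed, so a rise of 29 bpm counts the same as none. Second, each pools both directions. A drug that moves the whole distribution upward adds high events and removes low ones, and the pooled proportion may hardly move.

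Aim 4 hopes to find that the adverse event profile does not differ significantly from placebo, so an insensitive comparison leans toward the hoped-for answer. Potential Risks and Discomforts lists hemodynamic compromise among the most serious, dose-dependent risks of systemic absorption, and says no incidence data exist for prophylactic use. If the values are not written down at the time, a more sensitive analysis may not be recoverable later.

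**Working it through.** **The plan's own figure.** There is none to reproduce: "Formal power calculations are not possible as studies of this kind have not been previously performed".

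**Inputs from the documents.** The Overview says "In this trial, we intend to include a total of 100 procedures in the final analysis". The arm is chosen "based again on a computerized electric coin toss", so about 50 per arm is expected, not guaranteed. The significance level is 0.05; two-sided is assumed.

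**Assumed inputs, because the documents give none.** Baseline heart rate 90 bpm (SD 14); mean placebo peak 10 bpm above baseline; SD of peak 17; baseline–peak correlation r from 0.4 to 0.6; procedures independent; drug adds a constant shift.

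**Step 1: baseline-adjusted peak.** SE = 17 × √(1 − r²) × √(2/50).
- r = 0.4: 17 × 0.917 × 0.2 = 3.12. Power at 8 bpm ≈ Φ(8/3.12 − 1.96) = Φ(0.61) = 0.73.
- r = 0.6: 17 × 0.8 × 0.2 = 2.72. Power ≈ Φ(8/2.72 − 1.96) = Φ(0.98) = 0.84.

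Simulation (4,000 trials per setting) gives 72–83%. The 95% CI half-width is 1.96 × SE, about 5.3 to 6.1 bpm.

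**Step 2: rise-only event** (peak above 120, or a rise of 30 or more), Fisher's exact test, same simulated data.

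| True shift | Rise-only event | Adjusted peak |
|---|---|---|
| 6 bpm | 20–23% | 46–58% |
| 8 bpm | 36–41% | 72–83% |
| 10 bpm | 53–63% | 88–95% |
| 12 bpm | 74–80% | 97–99% |
| 15 bpm | 92–95% | about 100% |

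**Step 3: pooled event, as item 5 is written.** This needs a lowest heart rate as well. Assume it averages 6 bpm below baseline (SD of that change 8) and shifts equally with the drug. Its SD is √(14² + 8²) = 16.1.
- Baseline 90, shift 8: the chance of a lowest rate under 60 falls from Φ((60 − 84)/16.1) = 6.8% to Φ((60 − 92)/16.1) = 2.4%. Power for the pooled event is about 20%.
- Baseline 80, shift 8: low events fall from Φ((60 − 74)/16.1) = 19% to Φ((60 − 82)/16.1) = 8.6%, which largely offsets the extra high events. Power is about 4%, no better than chance.

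**Step 4: cross-check in closed form with other assumptions.** SD of change 15, shift 10, n = 50 per arm.
- Continuous: SE = 15 × 0.2 = 3; Φ(10/3 − 1.96) = Φ(1.37) = 0.915.
- Event (rise of 30 or more), placebo rising 10 on average: p₀ = 1 − Φ(20/15) = 9.1%, p₁ = 1 − Φ(10/15) = 25.2%. Power = Φ{[Δ − 1.96√(2p̄(1 − p̄)/n)] / √((p₀q₀ + p₁q₁)/n)} = Φ{(0.161 − 0.148)/0.0737} = Φ(0.18) = 0.57.
- The same event with no placebo rise: 2.3% against 9.1%, power 0.31.
- With a shift of 15 and placebo rising 10: 0.92 for the event against 0.999 for the continuous comparison.

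Both routes show a material loss at modest shifts that shrinks as the shift grows.

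**The case against.** The strongest reply is that Aim 4 asks for the prevalence of clinically significant change. A prevalence is a proportion, and items 5 and 6 answer it directly. A mean shift of 8 bpm could be detectable without any patient meeting the protocol's definition of harm. This stands: the continuous analysis should supplement the threshold events, not displace them. The trial is also a self-described pilot with no power target, so low power breaks no promise in the plan.

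Three stronger readings are tempting, and the documents do not support them.
- A reader might infer that the thresholds ignore the patient's own baseline. They do not: both items contain change-from-baseline limbs. What is lost is the size of the change.
- A reader might infer that a hemodynamic rise is the drug's most likely adverse effect. Potential Risks and Discomforts speaks of the most serious complications and expects lower systemic absorption with prophylactic use. The dog study of catheter instillation cited in the introduction found no significant heart rate change and minor falls in blood pressure. This is also a reason to look at lowest systolic pressure.
- A reader might infer that power is halved as a fixed fact. That ratio holds only near particular values of shift, SD and event rate.

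The general t-test and Mann-Whitney clause would permit a continuous comparison, and Safety Outcomes does draw on vital signs. But no heart rate or blood pressure variable is named for the clause, and no capture of one is specified.

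**Conclusion.** The point holds as a gap in sensitivity, not as an error in the defined outcomes. Items 5 and 6 match Aim 4, but nothing in the plan captures or compares how far heart rate or blood pressure moved, and pooling both directions can hide a uniform shift. For heart rate, under the assumptions listed, the rise-only event has roughly half the power of the adjusted comparison at 8 bpm. The gap is small by 15 bpm and wider once rises and falls are pooled. All sizes rest on assumed SDs, shifts and event rates and treat procedures as independent. Blood pressure has different cut-offs and was not calculated, so the heart rate figures should not be carried over to it. The change is worth making before data collection.

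**What to change.** 1. Keep items 5 and 6 as the clinical safety outcomes, and tabulate upward and downward events separately by arm.
2. Add to the case report form the last value before instillation, and the maximum and minimum within 30 minutes of first instillation, for heart rate, systolic and diastolic pressure.
3. Add a supplementary analysis of peak heart rate, peak systolic pressure and lowest systolic pressure. Regress each on arm and its pre-instillation value, and report the adjusted mean difference with 95% CI. The interval shows what size of shift is excluded, which a non-significant Fisher test does not.
4. Use standard errors that allow for several procedures in one patient, since Process of Obtaining Informed Consent expects repeat participation.
5. Note any open-label topical epinephrine given within the window when interpreting the result. If it is commoner on placebo, it could mask a difference.

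Cost: 3 variables × 3 values = 9 numbers per procedure, transcribed from monitoring already done, and a few extra regressions. No added patient burden.

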Local practices in University of Maryland Medical Center (UMMC) for the initial treatment of endobronchial bleeding in the bronchoscopy suite includes administration of iced saline in aliquots of 5-10 mL followed by 1-2 mL aliquots of 1:10,000 topical epinephrine (0.1-0.2 mg) to a maximum of 6 mL (0.6 mg). Additional suggested measures include positioning the patient with the bleeding lung in the dependent position and balloon tamponade of the bleeding airway with application of a 2-4 FR embolectomy balloon catheter (Edwards Lifesciences®) via the bronchoscope’s working channel before attempting more advanced methods to allow hemostasis.

The Role of Transbronchial Lung Biopsies in Lung Transplant Recipients

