 - 9.8. Date and time of scope insertion and completion of the procedure as defined by the performing bronchoscopist.
 - 9.9. Biopsy forceps brand, including outer diameter, open forceps diameter, and type of forceps (round cup, oval cup, alligator, impaling needle).
 - 9.10. Fluoroscopy time.
 - 9.11. Number of forceps passes.
 - 9.12. Total number of acquired biopsy specimens; Specimen distribution across laboratories (anatomic pathology, microbiology, other laboratory).
 - 9.13. Lobe and segment of each biopsy specimen.
 - 9.14. Any medical intervention performed in the bronchoscopy suite or in the recovery suite for stabilization of the patient’s medical condition during or following the procedure, including hemostasis, management of cardiac events, and management of respiratory events.

Outcome Measures

Primary Efficacy Outcome

The primary efficacy outcome of the PROPHET Study is the prevalence of major hemorrhage as defined by two independent reviewers who will review the procedure video while blinded to the individual patient information, study drug assignment, and any procedure related data not recorded on video. Hemorrhage will be graded according to a grading system suggested by

Pilarczyk *et al.* (43) and modified in accordance with the PROPHET Study scientific question as follows:

Grade	Description
No hemorrhage	No hemorrhage
Minor	Endobronchial hemorrhage resulting in segmental or more distal bronchus blood spillage
Intermediate	Endobronchial hemorrhage resulting in lobar bronchus blood spillage
Major	Endobronchial hemorrhage resulting in mainstem bronchus, more proximal blood spillage, or spillage into the uninvolved lung

Secondary Efficacy Outcomes

1. Occurrence of no, minor, or intermediate bleeding as defined by the independent reviewer.
2. Likert scale grading of bleeding by independent observer on a scale of 1 to 5:

1	2	3	4	5
Much less than usual for TBLB	Less than usual for TBLB	Usual for TBLB	More than usual for TBLB	Much more than usual for TBLB

3. Intra-procedural grading by the performing bronchoscopist according to procedure-related outcome as described by Ernst *et al.* and Herth *et al.* (31,44):

Grade	Description
No hemorrhage	No hemorrhage
Mild	Any bleeding originating from the biopsy target airway requiring wedging of the bronchoscope or “in and out” motion in order to achieve hemostasis

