Following retraction of the bronchoscope, fluoroscopy will be performed while the patient is still on the bronchoscopy bed in order to try and identify early pneumothorax. The patient will then be transferred for recovery in the UMMC endoscopy peri-procedure suite or in the admitting unit. A chest radiograph will be obtained to identify late pneumothorax within two hours of the termination of the procedure or later if late symptoms suggestive of pneumothorax appear. Also, a repeat ECG will be obtained within two hours of the termination of the procedure or earlier if symptoms suggestive of cardiac arrhythmia, ischemia, or conduction abnormality appear. The patient will also be assessed by a clinician to evaluate for signs and symptoms of pneumothorax or significant pulmonary hemorrhage on the same day of the procedure. Patients will be instructed not to drink or eat in the 2 hours following the procedure and if stable for discharge from the hospital on the same day of the procedure, to be driven to their place of residence by an escort. Patients will also be instructed to call if they had any hemoptysis, dyspnea, chest pain, or wished to ask questions.

Long-Term Post-Procedure Surveillance

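### Safety outcome 4 has a 30-minute window, but the one scheduled post-drug ECG may fall 90 minutes or more beyond it, and instillation time is not a listed data item

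*Combined protocol and SAP*

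**What the plan says.** **The window.** Safety Outcomes, item 4, groups ST change, ventricular and supraventricular arrhythmia, ectopy, bundle branch block and atrioventricular block, "all occurring within 30 minutes of the instillation of the study drug". ST change must appear in two or more "precordial or limb ECG leads that correspond together to one of the cardiac walls".

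**The scheduled tracing.** Immediate Post-Procedure Surveillance states that "a repeat ECG will be obtained within two hours of the termination of the procedure or earlier if symptoms suggestive of cardiac arrhythmia". Symptoms pointing to ischemia or a conduction problem bring it forward in the same way. No other post-drug ECG is scheduled.

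**Other monitoring.** Procedure Performance, item 3, requires a continuous rhythm strip. Initial Evaluation keeps participants on telemetry from intake until about an hour after the procedure. Item 9.6 makes the results study data: "Any hemodynamic, cardiac, or respiratory events as recorded by telemetry in the procedure suite" or in recovery. The lead-in to Safety Outcomes also names ECG recordings made during and just after the procedure as a source.

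**The clock.** Study drug goes in before the biopsies. Procedure Performance, item 7, adds: "This process may be repeated once, should the performing bronchoscopist choose to perform additional biopsy passes through a different airway". Of the data items that might carry a time, item 9.4 lists "Name and dosages of all medications administered to the patient in the hospital during the day of the procedure" and item 9.8 lists "Date and time of scope insertion and completion of the procedure as defined by the performing bronchoscopist". Neither lists the time of an instillation.

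**The concern.** An outcome defined by a short window needs an observation inside it and a known starting time. For two components of outcome 4 the plan secures neither. A site following the protocol exactly could take its only scheduled ECG after the window has closed.

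ST elevation is a harm the protocol itself cites: one published case followed 3 mL of 1:10,000 epinephrine. That patient had chest pain and was being treated for bleeding in friable airways, so the case shows plausibility and says nothing about a rate in prophylactic use. A similar case here would probably trigger an early ECG. A silent change in a patient sedated with midazolam and fentanyl might be missed, or seen later with no way to date it to the window.

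Rescue epinephrine complicates dating further. Local practice allows "1-2 mL aliquots of 1:10,000 topical epinephrine (0.1-0.2 mg) to a maximum of 6 mL (0.6 mg"), given open-label in either arm and possibly before the ECG. Without times, a change on a late tracing cannot be placed relative to study drug or rescue drug.

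The missing clock reaches past the ECG. Heart rate is monitored continuously and blood pressure every 3 minutes, but assigning a reading to the 30-minute window also needs the start time.

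**Working it through.** The plan gives no figure on this point to reproduce. The check is timing arithmetic and a comparison of sections.

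**1. Inputs**
- Window for outcome 4: 30 minutes from instillation (Safety Outcomes, item 4).
- ECG delay after the procedure ends, *u*: up to 120 minutes (Immediate Post-Procedure Surveillance).
- Time from last instillation to end of procedure, *x*: at least 0, because instillation precedes biopsy. The documents give no procedure duration, so *x* is varied. Counting from the last instillation is an assumption; counting from the first only widens the gap.

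**2. Latest permitted ECG**
- Time from instillation = *x* + 120 ≥ 120 minutes.
- Time past the window = *x* + 120 − 30 = *x* + 90 ≥ 90 minutes.

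**3. Share of the permitted 120 minutes that lies inside the window** = max(0, 30 − *x*)/120

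| *x* (assumed, min) | Share inside window | Latest ECG after instillation (min) |
|---|---|---|
| 0 | 30/120 = 25% | 120 |
| 10 | 20/120 = 17% | 130 |
| 20 | 10/120 = 8% | 140 |
| 30 | 0% | 150 |
| 40 | 0% | 160 |

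These are shares of permitted time. They are not probabilities that an ECG falls in the window, because actual ECG timing is unknown.

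**4. Which components are exposed**
- *Rhythm events and atrioventricular block.* Telemetry runs to about *x* + 60 minutes after instillation, which exceeds 30 for every *x*. Covered.
- *Symptomatic ischemia.* Symptoms bring the ECG forward, and outcome 2 separately counts new chest pain and acute myocardial ischemia within 30 minutes. Covered.
- *Silent ST change in two or more corresponding leads, and confirmation of bundle branch block.* These depend on which leads the monitor shows, which is not stated. Not secured.

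**5. How far the missing clock reaches**
- Outcome 1 is timed at 3 hours from instillation and outcomes 2 to 6 at 30 minutes, so all six need a start time.
- With two instillations allowed, the text does not say which one starts the window.
- Insertion time is recorded and the whole procedure is videoed, so instillation time could be recovered as insertion time plus elapsed video time. No step says to do this.

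**6. Doses in play**
- 1:10,000 is 0.1 mg/mL. One instillation: 2 × 0.1 = 0.2 mg; two: 0.4 mg. Cited case: 3 × 0.1 = 0.3 mg. Rescue maximum: 6 × 0.1 = 0.6 mg.

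**7. The fix checked**
- An ECG taken *u* minutes after the procedure is inside the window if *x* + *u* ≤ 30. If *u* ≤ 10 (assumption), it is always inside when *x* ≤ 20, and always outside when *x* > 30.

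**The case against.** The strongest reply is that the plan already names ECG recordings during the procedure as a source for the safety outcomes, and that outcome 4 accepts limb leads, which a monitor may show. Silence about leads does not prove that ST change cannot be read. This stands: it narrows the point to something the plan fails to secure, and does not show that observation is impossible.

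Second, the population is screened for ongoing ischemia, recent coronary events and low ejection fraction; epinephrine has a short half-life; and the protocol expects less absorption in prophylactic use. All fair. They make events less likely and give a plausible reason for a 30-minute window, but they do not bring the ECG into it.

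Third, changes found late are still recorded as adverse events. True, though whether they belong to outcome 4 is left open.

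Fourth, a zero count would be weakly reassuring anyway. With 50 epinephrine procedures (assumed half of 100, treated as independent), the one-sided 95% upper limit is 1 − 0.05^(1/50) = 5.8% even with perfect detection. This also stands. A reader might go on to inflate that limit for missed events, but the documents give no detection rate, so any such figure would be invented.

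A reader might also infer bias between arms. The ECG schedule is the same in both, so it does not itself favor either. Counting every change on the first post-procedure ECG within outcome 4 is another tempting step. That would admit effects of rescue epinephrine, and if prophylaxis works the placebo arm may receive more rescue, which could make study drug look safer.

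**Conclusion.** The point holds in a limited form. Following the plan exactly can put the only scheduled post-drug ECG 90 minutes or more beyond the window of the outcome it should inform. The exposed components are silent multi-lead ST change and confirmation of bundle branch block. Separately, none of the six safety outcomes has a recorded starting time.

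The 90-minute figure is for the latest permitted ECG; the wording also permits one inside the window. It assumes only that instillation does not come after the end of the procedure. How many events might be missed cannot be estimated from the documents.

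The documents do not support reading this as a failure of cardiac safety monitoring in general, since arrhythmia and symptomatic ischemia are covered. The consequence is that the ST and bundle branch block counts may be too low and some events undatable. Aim 4 is exploratory, so the impact is modest, but the correction is cheap and worth making.

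**What to change.** - Take the existing repeat ECG as a 12-lead as soon as the patient reaches recovery, after the pneumothorax fluoroscopy, and within 30 minutes of the last instillation where feasible. Keep the symptom-triggered ECG.
- Record the clock times of each instillation, any rescue epinephrine and the ECG.
- State which instillation starts the window, and which leads are monitored during the procedure.
- Keep the 30-minute definition of outcome 4. Report ST change or bundle branch block first seen on a later ECG separately, with its time from study drug and from any rescue epinephrine.
- Editorial: add the repeat ECG to the Day 0, time 0 to +3 row of Study Flow (Outpatients), which lists the chest radiograph but not the ECG.

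**Cost.** No extra test: the same ECG earlier, three kinds of time entry on the case report form, and a few sentences. The downside is a slightly lower chance of catching late-onset change on the single scheduled tracing, partly offset by about an hour of telemetry after the procedure. In a long procedure the tracing can still miss the window, which is why its time from instillation should be reported.
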